5.3.4. Collection of Pregnancy Information

5.3.4.1. Male participants with partners who become pregnant

- The Investigator will attempt to collect pregnancy information on any male participant's female partner who becomes pregnant while the male participant is in the first 29 days of this study.
- After obtaining the necessary signed informed consent from the pregnant female partner directly, the Investigator will record pregnancy information on the appropriate form and submit it to the Sponsor within 24 hours of learning of the partner's pregnancy.
- The female partner will also be followed to determine the outcome of the pregnancy. Information on the status of the mother and child will be forwarded to the Sponsor. Generally, the follow-up will be no longer than two months following the estimated delivery date. Any termination of the pregnancy will be reported regardless of fetal status (presence or absence of anomalies) or indication for the procedure.

5.3.4.2. Female participants who become pregnant

- The Investigator will collect pregnancy information on any female participant who becomes pregnant while participating in this study. The initial information will be recorded on the Pregnancy Report Form and submitted to the Sponsor within 24 hours of learning of a participant's pregnancy.
- The participant will be followed to determine the outcome of the pregnancy. The Investigator will collect follow-up information on the participant and the neonate and the information will be forwarded to the Sponsor. Generally, follow-up will not be required for longer than twelve months beyond the estimated delivery date. Any termination of pregnancy will be reported, regardless of fetal status (presence or absence of anomalies) or indication for the procedure.
- While pregnancy itself is not considered to be an AE or SAE, any pregnancy complication or elective termination of a pregnancy for medical reasons will be reported as an AE or SAE (Section 6.7).
- A spontaneous abortion (occurring at < 22 weeks gestational age) or still birth (occurring at > 22 weeks gestational age) is always considered to be an SAE and will be reported as such.
- Any poststudy pregnancy related SAE considered reasonably related to the study intervention by the Investigator will be reported to the Sponsor. While the Investigator is not obligated to actively seek this information in former study participants, he or she may learn of an SAE through spontaneous reporting.
- Details of all pregnancies in female participants and, if indicated, female partners of male participants will be collected after the start of study intervention and until EOS or ET.
- If a pregnancy is reported, the Investigator should inform the Sponsor within 24 hours of learning of the pregnancy and should follow the procedures outlined in this section.
- Abnormal pregnancy outcomes (e.g., spontaneous abortion, fetal death, stillbirth, congenital anomalies, ectopic pregnancy) are considered SAEs. Therefore, they follow the same reporting requirements.

5.4. SUBJECT MEMORY AID COMPLETION

Memory Aids will be provided to subjects following the injection and subjects will be instructed in their use. On a daily basis during the 14-day period after the injection, then 3 times a week until day 29, then once a week until the end of the study, subjects will evaluate, record, and grade any local injection-site reactions (e.g., redness, swelling, tenderness, or pain), any general symptoms (e.g., fever, chills, sweat, myalgia, arthralgia, fatigue, skin or mucosal lesions, or gastrointestinal symptoms), and any neurological signs and symptoms (blurry vision, changes in balance or coordination, confusion, disorientation, dizziness, severe headache, shaking or body tremors, slurred speech, tingling or numbness, weakness or feeling weak). These types of neurological symptoms should be evaluated within 24 hours. To more accurately account for the size of any local reactions, a ruler will be given to the subjects, and they will be instructed on how to use it. To more accurately account for possible fevers, subjects will be given an oral thermometer, instructed on its use, and asked to take and record their temperature on the same schedule.

Memory Aids will be reviewed by site staff at each follow-up visit during the post-injection period. If Memory Aids are not completed or returned, the Investigator will review the symptoms that occurred during that timeframe to the best of the subject's recollection to determine AEs and the subject will be retrained.

Although subjects will be instructed on the use of the Memory Aid and they are encouraged to fill it out as directed, although if it is not completed it will not be considered a protocol deviation. The information, if available, will be reviewed with the subject, and any positive responses confirmed. There will be three distinct Memory Aid periods:

5.4.1. Memory Aid / Period 1: Days 1-29

The Memory Aid for days 1-29 will ask subjects to record and grade the severity of local and systemic symptoms; grade and measure local injection-site reactions (redness, swelling, tenderness, and pain); body temperature; and concomitant medications. The Memory Aid for Days 16-29 will ask subjects to record any symptoms of arthritis (joint aches/pain [general or while moving joints] or joint swelling), and location of affected joint(s), as well as mouth ulcers, mucosal lesions, or dermatologic reactions such as rash, and neurologic symptoms.

The information will be reviewed with the subject and any positive responses confirmed. The Memory Aid includes a scripted section for solicited symptoms and a general question to elicit any unforeseen symptoms. If a symptom is reported by telephone that makes a personal contact desirable, an unscheduled optional visit can be performed at any time. Subjects who develop arthritic events or rash will be followed up until resolution of the AE.

5.4.2. Memory Aid / Period 2 and 3: Days 29-85, 85-181

The Memory Aid for days 29-85 and 85-181 will ask subjects to record and grade symptoms, MAAEs, SAEs, any important changes in health status, along with concomitant medications. All subjects will be followed until at least day 181. Subjects who develop arthritic events or rash requiring evaluation will be followed up until resolution of the AE. The information, if available on the Memory Aid, will be reviewed with the subject, and any issues considered to be AEs will be transcribed into the source documents for inclusion in the eCRFs.

5.5. SAFETY LABORATORY AND IMMUNOGENICITY ASSESSMENTS

5.5.1. Safety Laboratory Assessments

Safety laboratory assessments will be performed by the site's local laboratory. If an AE on day 5 or later post-vaccination of arthritis or petechial/purpuric or vesicular rash is reported at any follow-up visit, additional blood (i.e., chemistries and rheumatology panel) and urine will be obtained from the subject for laboratory testing. Repeat laboratory testing will be conducted as outlined in Section 6.1 and graded according to APPENDIX 1. Details regarding collection and processing of subject samples will be provided in the Study Procedure Manual.

Subjects will have blood, saliva, and urine assessed for evidence of rVSV via RT-qPCR. Plasma and urine samples for rVSV PCR will be collected and stored frozen until they are transferred for analysis. Saliva samples will be collected with an oral swab, placed in storage reagent, and stored frozen pending transport.

5.5.2. Blood for Immunogenicity Assessment and Vaccinemia

A blood sample for antibody tests will be drawn to obtain the minimum required serum volume for immunological assays and vaccinemia determinations (Table 3). All sample analysis will be performed at a laboratory designated by PHV.

Detailed instructions for separating serum and plasma, labeling, storage, and shipping of serum samples are included in the Laboratory Manual, provided separately. This will include the collection of blood (100 mL) for large volume serum on day 85.

5.5.3. Blood for Investigation of Post-Vaccination Arthritis and Post-Vaccination Rash (Rheumatology Panel)

In the event of a case diagnosed as post-vaccination arthralgia/arthritis or petechial, purpuric, or vesicular rash occurring on or after day 5, specific samples of blood are drawn at time of diagnosis. In addition, these same samples may be drawn more frequently as needed, depending upon symptoms, and will be run only in the event of the occurrence of either event, according to specific guidelines in Figure 2 and Figure 3.

5.6. METHODS/TIMING FOR ASSESSING, RECORDING, AND ANALYZING IMMUNOGENICITY MEASUREMENTS

5.6.1. Determining Antibody Titers of Study Subjects

Sera for immunogenicity will be collected as outlined in the Schedule of Events (Table 2).

5.6.2. Immunogenicity Measurement

Anti-PHV01 IgG titers will be determined by conventional ELISA utilizing recombinant Marburg GP as the antigen. Anti-PHV01 neutralizing antibodies will be determined as measured by PsVNA.

5.6.3. Exploratory Measurements

There are multiple exploratory endpoints related to the immunological response to the vaccine. At the discretion of the Sponsor, additional immunology tests may be performed for exploratory purposes:

- Wild-type Marburg neutralization against one or more Marburg lineages
- Marburg ELISA against one or more Marburg lineages
- Determination of Fc-mediated cell-targeting antibodies, e.g., ADCC, ADNP, ADMP, etc.
- T-cell responses to Marburg GP protein by intracellular cytokine staining (ICS) and/or enzyme-linked immune absorbent spot (ELISPOT)
- Determination of Marburg IgM ELISA antibody responses
- Determination of pro-inflammatory markers, such as CRP, ICAM-1, VCAM-1 levels, and cytokine levels
- Determination of gene activation by RNA transcript sequencing (transcriptomics)
- Determination of B or T cell responses to VSV proteins

5.6.4. Vaccinemia and Shedding

Vaccinemia and shedding will be determined by PHV01 RT-qPCR assay using primer-probe set(s) specific for the vaccine vector VSV.

6. SAFETY ASSESSMENT

Safety monitoring will be conducted throughout the study; therefore, safety concerns will be identified by continuous review of the data by the PI, clinic staff, Medical Monitor, and Sponsor.

An SRC will be chartered by the Sponsor to monitor human subject safety during the study and will review any safety concern. Significant issues will be conveyed to the IRB.

6.1. ASSESSMENT OF SAFETY

All AEs will be assessed as described in Section 6.4 according to the FDA document "Guidance for Industry: Toxicity Grading Scale for Healthy Adult and Adolescent Volunteers Enrolled in Preventive Vaccine Clinical Trials" (37), using toxicity grading tables excerpted from that guidance shown in APPENDIX 1: Clinical and Laboratory Toxicity Grading, Tables A1-A3. Safety will be assessed by evaluating reactogenicity (local reactions and systemic reactions) and the occurrence of post-vaccination solicited local reactions and systemic AEs through day 15. Solicited AEs for days 16-29 are limited to instances of neurological signs and symptoms, arthritis, and rash. Arthritis, rash, and neurologic events should be evaluated throughout the study and may include expert consultation.

Grading scales for laboratory value abnormalities are shown in APPENDIX 1: Clinical and Laboratory Toxicity Grading, Tables A4 and A5. Local laboratory normal ranges will be used to classify laboratory results. Clinically significant abnormal laboratory values will be graded as AEs according to the ranges specified in the table.

All vaccine-related SAEs must be reported as soon as possible following confirmation. The toxicity grading tables should be followed when determining the severity of an SAE.

Signs and symptoms of an AESI, as listed in Section 6.4.3, will be assessed throughout the study. If neurologic symptoms are present, a neurologic examination should be performed and documented. Neurologic examinations will also be performed at baseline and day 29.

The nature, frequency, and severity of MAAEs and SAEs from the time of injection through the final study visit should be recorded for each subject. MAAEs are defined as AEs leading to medically-attended visits that were not a routine visit for physical examination or vaccination, such as an emergency room visit or an otherwise unscheduled visit to or from medical personnel (medical doctor) for any reason.

6.2. ASSESSMENT OF SUBJECTS WITH JOINT-RELATED ADVERSE EVENTS

In the event of cases of acute aseptic arthritis, data collection, analysis, and presentation should be performed in accordance with Brighton collaboration guidelines (45) and may require expert consultation.

Subjects who have joint pain on or after day 6 following administration of vaccine will undergo assessment by the PI within 72 hours of onset with a targeted exam, guided by the Arthritis Pathway titled "Evaluation of Subjects with Joint Signs and Symptoms" (Figure 2). In brief:

• The subject self-monitors for joint pain or rash. The subject should identify the primary source of pain and any other affected joints.

- Determine if findings of arthritis are present, defined as any 1 of the following:
 - o Clinically significant reduction in range of motion
 - o Synovitis (tenderness or swelling or redness or heat)
 - o Effusion
- Document findings using the standardized form.
- If arthritis present, draw a CBC, serum chemistries (including BUN, creatinine, and uric acid), PT/PTT, fibrinogen, a rheumatology panel (CRP, RF, anti-CCP, C3, C4, ANA, anti-CCP, sample for cytokine levels), and obtain a urinalysis.

If arthritis is present, the subject should be assessed either by a Physician Investigator who is proficient in arthrocentesis or a consultant. If effusion is confirmed, consent should be obtained for the subject to undergo arthrocentesis for joint fluid assessment.

[figure not shown]
- The synovial fluid assessment should include:
 - Cell count with differential
 - o Crystal examination
 - o Culture for bacteria, and virus isolation
 - o RT-qPCR for vaccine viral RNA

Follow-up is determined by clinical course. If symptoms are mild (Grade 1), follow up as per Schedule of Events: days 8, 15, and 29, then monthly until resolved. If at day 29 the ongoing symptoms are Grade 2 or worse, follow weekly until mild (Grade 1) and then schedule as above. Repeat BUN, creatinine, uric acid, and rheumatology panel, and obtain urinalysis at follow up visits until resolved. The Investigator may evaluate the subject more frequently if clinically indicated.

If rash is present on any visit, this triggers the Dermatology Pathway, as outlined in Section 6.3.

Figure 2: Evaluation of Subjects with Joint Signs and Symptoms

6.3. ASSESSMENT OF SUBJECTS WITH DERMATOLOGIC ADVERSE EVENTS

In the event of rash, including mucosal involvement, evaluation, data collection, and analysis will be performed in accordance with Brighton collaboration guidelines (46). Any new rash will be investigated and reported by the PI within 72 hours of onset.

Subjects who develop a rash following administration of vaccine will undergo assessment by a Physician Investigator at each site. The Investigator's assessment will be guided by the "Evaluation and Work-Up of Adverse Event of Petechial/Purpuric/Vesicular Type Rash" (Figure 3). In brief:

- Subject self-monitors for rash or mucosal lesions with onset on or after day 5.
- Physician Investigator assesses skin to determine if significant findings are present:
 - o Petechiae, Purpura, and/or Vesicles
 - Mucosal lesions
 - o Urticaria
 - o Other

[figure not shown]
- Document the examination in the eCRF and photograph the lesions.
- If petechial, purpuric, or vesicular rash is present, draw CBC, serum chemistries (BUN, creatinine, uric acid), PT/PTT, fibrinogen, and rheumatology panel (CRP, RFF, anti-CCP, C3, C4, ANA, and a sample for cytokines), and obtain urinalysis.
 - If the subject is amenable, the Physician Investigator should obtain informed consent and perform 1-2 punch biopsies. Portions of the biopsy should be Formalin fixed and stained for H&E, immune complex deposition, and immune-stained for VSV and/or MARV GP.
 - Placed into RNA Later for processing to do RT-qPCR (see Laboratory Manual).
- Refer to Dermatologist for additional specialty consultation within 72 hours if possible.

Follow-up is determined by clinical course. If symptoms are mild (Grade 1) and participant stable or improving, follow up per SoE, i.e., days 8, 15, and 29, then monthly until resolved. If at day 29, ongoing symptoms are moderate (Grade 2) or worse, follow weekly until mild and then schedule as above. The Investigator will evaluate the subject more frequently if clinically indicated.

If arthralgia/arthritis is present on any visit on or after day 5 this triggers the Arthralgia Pathway as outlined in Section 6.2.

Figure 3: Evaluation and Work-Up of Adverse Events of All Rashes of Concern

6.4. IND SAFETY REPORTING

The terms described below, as defined by 21 Code of Federal Regulation (CFR) Part 312.32, apply to IND safety reporting.

6.4.1. Adverse Event or Suspected Adverse Reaction

An AE is defined as any untoward medical occurrence associated with the use of a pharmaceutical product in humans, whether considered product-related or not. An AE can therefore be any unfavorable and unintended sign (including an abnormal laboratory finding), symptom, or disease temporally associated with the use of a medicinal (investigational) product, regardless of whether it is related to the medicinal (investigational) product. This definition includes intercurrent illnesses or injuries and exacerbation of pre-existing conditions.

A suspected adverse reaction is defined as any AE for which there is a reasonable possibility that the product caused the AE. For the purposes of IND safety reporting, "reasonable possibility" means there is evidence to suggest a causal relationship between the product and the AE. "Suspected adverse reaction" implies less certainty about causality than "adverse reaction", which

means any AE caused by a product. An AE is any adverse change or exacerbation from a baseline condition which occurs following the initial administration of an IP, whether or not the event is considered to be related to the IP. Examples of this include but are not limited to the following:

- Adverse changes, including new signs and symptoms, intercurrent illness modifying the clinical course, or the worsening of a baseline condition, including the increased frequency of an event or increased intensity of a condition.
- Concomitant disease with onset or increased severity after the start of study product administration.
- A new pattern in a pre-existing condition, occurring after the receipt of IP, that may signal a clinically meaningful change.
- Any abnormal laboratory value, whether clinically significant or not.

All AEs will be monitored until resolution or, if the AE becomes chronic, a cause is identified. If an AE is unresolved at the conclusion of the study, a clinical assessment will be made by the Investigator or Medical Monitor whether continued follow-up of the AE is warranted. The severity of events will be determined by the Investigator as described in Section 6.5.

The Investigator must assign a relationship of each AE to the receipt of the IP. The Investigator will use clinical judgment in conjunction with the assessment of a plausible biologic mechanism, a temporal relationship between the onset of the event in relation to receipt of the IP, and identification of possible alternate etiologies including underlying disease, concurrent illness, or concomitant medications. The following guidelines should be used by Investigators to assess the relationship of an AE to study product administration. **ONLY A LICENSED PHYSICIAN CAN MAKE THIS DETERMINATION.**

Not related: No relationship to IP. Applies to those events for which evidence exists that there is an alternate etiology.

Possible: An association between the event and the administration of IP cannot be ruled out. There is a reasonable temporal association, but there may also be an alternative etiology such as the subject's clinical status or underlying factors including other therapy.

Probable: There is a high degree of certainty that a relationship to the IP exists. There is a reasonable temporal association, and the event cannot be explained by known characteristics of the subject's clinical state or factors including other therapy.

Definite: An association exists between the receipt of IP and the event. An association to other factors has been ruled out.

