1.5. KNOWN AND POTENTIAL RISKS AND BENEFITS TO HUMAN SUBJECTS

1.5.1. Risks/Discomfort to Subjects and Precautions to Minimize Risk

This will be the first clinical trial involving PHV01 vaccine candidate administration to humans in the US under an Investigational New Drug (IND) application with FDA.

Potential risks associated with this vaccine may include those common to other vaccine products, including local injection site reactions and systemic reactions. The following sections discuss these potential risks in more detail and include brief descriptions for possible procedures to ameliorate risks and symptoms. All relevant risks and precautions are described and explained in detail in the Informed Consent Form (ICF) provided to potential subjects.

It is possible that the side effects of PHV01 will be improved by lowering the dose administered.

Local Reactions

In a study of the only licensed rVSV-based vaccine, rVSVΔG-ZEBOV-GP (ERVEBO) (N=1051) versus placebo (N=133) in healthy North American adult subjects, the most common AEs were injection site pain (69.5% vs 12.8%), swelling (16.5% vs 3.0%), and redness (11.9% vs 1.5%) (17). Similar local injection site reactions, with either PHV01 or placebo, may include pain, swelling, and/or redness at the injection site. Although highly unlikely, IM injections, even

independent of investigational product (IP), can result in acute muscle damage, bruising, and/or injection site infection.

Early Systemic Reactions

Transient mild to moderate lymphopenia and neutropenia have been described after receipt of $\text{rVSV}\Delta\text{G-ZEBOV-GP}$ and are similar to findings associated with acute viral infections. No associated infections have been reported. Similar hematologic effects may be seen with PHV01.

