3.7.2. Stopping and Pausing Rules

Criteria for Study Pause or Halt

Study pause and halting criteria related to AEs are as follows:

The SRC will review the day 8 safety data in each Dosing Cohort to determine if enrollment may continue.

Dosing will be paused if 2 or more subjects experience the same or similar Grade 3 adverse event considered to be at least possibly related to vaccination. In the event of a study pause, the SRC will meet before resumption of dosing.

Dosing will be halted if a SAE or an AESI is considered anything other than not related to PHV01 vaccine. In the event dosing is halted, the SRC and IRB will review the event and other relevant safety data from the study and the IRB must agree before any continuation of dosing.

Enrollment

If no pause or halting rules are triggered in each Dosing Cohort, enrollment and dosing may proceed after review of day 8 safety data by the SRC. In the event dosing is paused or halted, scheduled follow up visits and procedures will continue for subjects already dosed.

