6.4.3. Adverse Events of Special Interest

The following are AESIs that will be monitored with increased frequency for safety purposes. AESIs that meet the serious criteria as defined in Section 6.4.4 will be reported as SAEs.

Respiratory Events:

• Acute respiratory distress syndrome/pneumonitis

Neurologic Events:

- ADEM
- Aseptic meningitis
- Encephalitis
- Generalized convulsions
- GBS
- Myelitis
 - o Optic neuritis
 - Transverse myelitis

Hematologic Events:

• Thrombocytopenia ≥ Grade 2

Immunologic Events:

- Anaphylaxis
- Vasculitides

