6.5. SEVERITY ASSESSMENT

All AEs will be assessed for severity by the Investigator. Inherent in this assessment is the medical and clinical consideration of all information surrounding the event, including any medical intervention required. Each event will be assigned one of the following categories: mild, moderate, severe, or life-threatening. Refer to the grading scale in APPENDIX 1 for further guidance in the assignment of severity. Any Grade 4 (life-threatening) AE must be reported as an SAE.

The eCRF for AEs will reflect only the highest severity for continuous days an event occurred. The following criteria below may be used for any symptom not included in the grading scale:

Mild (Grade 1): Does not interfere with routine activities; minimal level of discomfort.

Moderate (Grade 2): Interferes with routine activities; moderate level of discomfort.

Severe (Grade 3): Unable to perform routine activities; significant level of discomfort.

Potentially life-threatening (Grade 4): Hospitalization or ER visit for potentially life-threatening event.

The FDA guidelines for toxicity will be followed; however, if a subject is evaluated in an emergency room for nonlife threatening illness or symptoms (i.e., visits emergency department on weekend for mild problems because the physician's office is closed), the information from that visit will be reviewed and severity of the AE will be assessed according to the subject's clinical signs and symptoms.

As defined by the ICH guideline for GCP, the term "severe" is often used to describe intensity (severity) of a specific event (as in mild, moderate, or severe myocardial infarction); the event itself, however, may be of relatively minor medical significance (such as severe headache). This is **not** the same as "serious", which is based on subject/event **outcome** or **action** criteria usually associated with events that pose a threat to a subject's life or functioning. Seriousness (not severity) serves as a guide for defining regulatory reporting obligations.

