Hemoglobin (Male) - gm/dL	12.5 - 13.5	10.5 - 12.4	8.5 - 10.4	< 8.5
WBC Increase - cell/mm ³	10,800 – 15,000	15,001 – 20,000	20,001 - 25, 000	> 25,000
WBC Decrease - cell/mm ³	2,500 - 3,500	1,500 - 2,499	1,000 - 1,499	< 1,000
Lymphocytes Decrease - cell/mm ³	750 – 1,000	500 – 749	250 – 499	< 250
Neutrophils Decrease - cell/mm ³	1,000 – 1,499	500-999	<500	Hospitalization
Eosinophils - cell/mm ³	650 - 1500	1501 - 5000	> 5000	Hospitalization
Platelets Decreased - cell/mm ³	125,000 – 140,000	100,000 – 124,000	25,000 – 99,000	< 25,000

Abbreviations: ULN = upper limit of normal; WBC = white blood cell.

^b Oral temperature, no recent hot or cold beverages or smoking.

 $^{^{\}rm c}$ When resting heart rate is between 60-100 beats per minute. Use clinical judgement when characterizing bradycardia among some healthy subject populations, for example, conditioned athletes.

^a The laboratory values provided in the tables serve as guidelines and are dependent upon institutional normal parameters. The clinical signs or symptoms associated with laboratory abnormalities may result in characterization of the laboratory abnormalities as AEs if they are considered to be clinically significant.

Table A5: Laboratory Toxicity Grading Scale for Blood Chemistry and Urinalysis Adverse Events

Serum ^{a,b}	Mild (Grade 1)	Moderate (Grade 2)	Severe (Grade 3)	Potentially Life Threatening (Grade 4)
Blood Urea Nitrogen BUN (mg/dL)	23-26	27 – 31	> 31	Requires dialysis
Creatinine (mg/dL)	1.5 - 1.7	1.8 - 2.0	2.1 - 2.5	> 2.5 or requires dialysis
Glucose – Hypoglycemia mg/dL	65 – 69	55 – 64	45 – 54	< 45
Glucose – Hyperglycemia Fasting – mg/dL Random – mg/dL	100 – 110 110 – 125	111 – 125 126 – 200	>125 >200	Insulin requirements or hyperosmolar coma
Liver Function Tests – ALT, AST	1.1 – 2.5 × ULN	$2.6 - 5.0 \times ULN$	5.1 – 10 × ULN	> 10 x ULN
Bilirubin –accompanied by any increased LFT	1.1 – 1.25 x ULN	1.26 – 1.5 x ULN	1.51 – 1.75 x ULN	> 1.75 x ULN
Bilirubin – when LFT is normal	1.1 – 1.5 x ULN	1.6 – 2.0 x ULN	2.0 - 3.0 x ULN	> 3.0 x ULN
Urine Protein	Trace	1+	2+	Hospitalization for dialysis
Urine Glucose	Trace	1+	2+	Hospitalization for hyperglycemia
Blood (microscopic) RBCs / high power field ^c	1-10	11-50	>50 and/or gross blood	Hospitalization for pRBC transfusion

Abbreviations: ALT = alanine aminotransferase; AST = aspartate aminotransferase; BUN = blood urea nitrogen; PRBC = packed red blood cells; RBC = red blood cell; ULN = upper limit of normal

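### Protocol 6.4.1 and 6.1 disagree on whether a laboratory value judged not clinically significant is an AE, so the 3.7.2 pause and halt rules can give two answers

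*Protocol*

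**What the plan says.** Two rules for laboratory AEs stand in the current protocol.

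- **Broad.** Section 6.4.1, in its examples of adverse changes from baseline, lists "Any abnormal laboratory value, whether clinically significant or not".
- **Narrow.** Section 6.1 states: "Clinically significant abnormal laboratory values will be graded as AEs according to the ranges specified in the table". The footnotes to Tables A4 and A5, repeated in SAP Section 5, say that signs or symptoms accompanying an abnormality "may result in characterization of the laboratory abnormalities as AEs if they are considered to be clinically significant".

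The dosing rules in 3.7.2 are written in terms of AEs, SAEs and AESIs:

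- **Pause:** "Dosing will be paused if 2 or more subjects experience the same or similar Grade 3 adverse event", if at least possibly related. The SRC must then meet before dosing resumes.
- **Halt:** "Dosing will be halted if a SAE or an AESI is considered anything other than not related to PHV01 vaccine". The IRB must then agree before dosing continues.

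Section 6.5 links laboratory grades to the halt: "Any Grade 4 (life-threatening) AE must be reported as an SAE". One laboratory event has its own route. Section 6.4.3 lists "Thrombocytopenia ≥ Grade 2" as an AESI, defined by grade alone.

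**The concern.** In a first-in-human dose escalation, the stopping rules should give one answer for one set of data. Here the same laboratory result can require a stop under one section and not under another, and the investigator's view of clinical significance decides the matter only if 6.1 is followed.

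The situation is foreseeable. Section 1.5.1 reports for the related Ebola vaccine: "Transient mild to moderate lymphopenia and neutropenia have been described after receipt of" it, and adds that similar effects may be seen with PHV01. The SRC sees the Day 4 and Day 8 laboratory results at its Day 8 review, so no result is hidden. What is unsettled is whether stopping is mandatory or left to judgement. A smaller consequence is that counts of unsolicited AEs to Day 29, a primary safety endpoint in 3.1.1, depend on which section the site applies.

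**Working it through.** The plan gives no operating characteristic for the pause or halt rule, so there is no figure to reproduce. The check is textual, followed by an illustration of size.

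**1. The same result under each rule.** Each value is taken as worsened from baseline, possibly related and judged not clinically significant. Cut-offs are from Table A4.

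| Result | Under 6.4.1 | Under 6.1 |
|---|---|---|
| Lymphocytes 250–499/mm³ in two subjects | Two Grade 3 AEs: pause | No AE: no pause |
| Lymphocytes <250/mm³ in one subject | Grade 4 AE, SAE by 6.5: halt | No AE: no halt |
| PT >1.25 × ULN in one subject | Grade 4 AE, SAE by 6.5: halt | No AE: no halt |
| Platelets 100,000–124,000/mm³ in one subject | AESI by 6.4.3: halt | AESI by 6.4.3: halt |

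The platelet row reads 6.4.3 as applying by grade whatever the clinical significance, which is how the list is written.

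**2. Does anything set precedence?** Section 6.4 opens by tying its terms to IND safety reporting, which might confine 6.4.1. But 6.1 sends the assessment of all AEs to 6.4, and the relatedness categories, AESI list and SAE criteria that 3.7.2 needs are set out in 6.4. No other AE definition is supplied for 3.7.2. Section 3.1.3 has laboratory values graded but does not say that a graded value is an AE. The SAP repeats the footnotes and does not resolve the point.

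**3. Does relatedness remove the problem?** No. Section 6.4.1 reserves the not-related category for events with evidence of another cause, so an unexplained fall after dosing tends toward possible, which satisfies both rules.

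**4. Size for the pause.** Vaccinees per dosing cohort (Protocol 1.6, SAP Table 1-1) are 3, 7 + 3 = 10, 7 + 3 = 10, and 7. Cohorts 1 to 3, after which there is still a cohort to withhold, hold 3 + 10 + 10 = 23. Let p be the assumed proportion of vaccinees with the same possibly related Grade 3 abnormality:

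P(X ≥ 2) = 1 − (1 − p)^23 − 23p(1 − p)^22

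- p = 0.01: 1 − 0.794 − 0.184 = 0.022
- p = 0.05: 1 − 0.307 − 0.372 = 0.321
- p = 0.10: 1 − 0.089 − 0.226 = 0.685

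These are the chances that the definition decides the pause if every such value is judged not clinically significant. If a fraction s is judged significant, those values count under both rules, and the chance becomes P(X ≥ 2 at p) − P(X ≥ 2 at sp):

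| p | s = 0 | s = 0.5 | s = 0.8 |
|---|---|---|---|
| 0.01 | 2% | 0.022 − 0.006 = 1.6% | 0.0220 − 0.0145 = 0.8% |
| 0.05 | 32% | 0.321 − 0.112 = 21% | 0.321 − 0.234 = 9% |
| 0.10 | 68% | 0.685 − 0.321 = 36% | 0.685 − 0.559 = 13% |

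**5. Size for the halt.** One Grade 4 value suffices. With q the assumed proportion of vaccinees with a possibly related Grade 4 value judged not clinically significant, the chance of at least one among 23 is 1 − (1 − q)^23: 2.3% at q = 0.001 and 20.6% at q = 0.01.

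**The case against.** The best defence is that 6.4.1 is the outlier. Section 6.1 is the specific rule for laboratory values, the footnotes in both documents side with it, and the scope of 6.4 is stated as IND reporting. This is a sensible guess at what was intended, and it supports aligning 6.4.1 to 6.1 rather than the reverse. It does not settle the matter, for the reasons in step 2 of the working. The footnotes are also permissive rather than prescriptive, so the firm conflict is between 6.4.1 and 6.1.

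Several further points stand and limit the size of the problem:

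- Neither rule is mechanical. A physician judges relatedness, the investigator assigns severity on all the information, and Appendix 1 calls its cut-offs guidelines.
- A pause adds little to the Day 8 SRC review already required before the next cohort. The halt, which needs IRB agreement, differs more.
- Abnormal laboratory values form part of a primary safety endpoint of their own and are summarised by toxicity grade (Protocol 7.5.1, SAP 4.4.5). No laboratory information is lost.

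A reader might infer that 6.4.1 would flood the unsolicited AE tables, with one AE for every out-of-range post-dose result. The documents do not support that. The bullet sits under adverse changes from baseline, the eCRF keeps only the highest severity over continuous days (6.5), and SAP 4.4.2 counts each subject once per incidence rate.

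**Conclusion.** The contradiction is real and unresolved. A possibly related Grade 3 or 4 laboratory value judged not clinically significant does or does not trigger a mandatory pause or halt, depending on the section followed. Thrombocytopenia of Grade 2 or higher falls outside the ambiguity.

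The chance that the definition decides a pause in Cohorts 1 to 3 is at most 2%, 32% or 68% at assumed rates of 1%, 5% or 10%. It is lower if some of the values are judged clinically significant. The figures are for one laboratory abnormality, treat vaccinees as independent with a common rate across doses, and leave out placebo recipients. The low end is more plausible, because the effect described for the related vaccine is mild to moderate.

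A reader might take 68% as the expected chance of a disputed pause, or suppose that every symptom-free Grade 3 or 4 value is in dispute. Neither follows. The rates are assumptions, and an investigator may call a symptom-free value clinically significant, in which case both rules agree. The main consequence is for the dosing rules; the effect on unsolicited AE counts is secondary. The text should be corrected, but the finding does not show that the trial lacks safety oversight.

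**What to change.** 1. **Protocol 6.4.1.** Replace the bullet with: *An abnormal laboratory value, changed from baseline, judged clinically significant by the Investigator.* This matches 6.1, Appendix 1 and SAP Section 5. Make the mention of laboratory findings in the opening definition of 6.4.1 subject to the same condition.
2. **Protocol 3.7.2.** Add: *Any post-vaccination laboratory value of Grade 3 or higher that worsened from baseline is assessed for relatedness. If at least possibly related, it counts toward the pause rule whether or not it is judged clinically significant, and no repeat test is needed before pausing. Thrombocytopenia of Grade 2 or higher counts toward the halt rule as an AESI.*
3. **Protocol 6.5.** Add: *A Grade 4 laboratory value without clinical findings is an SAE only if it meets a criterion in 6.4.4. One such value, if at least possibly related, pauses dosing for SRC review.*
4. **SAP 4.4.2.** Repeat the laboratory AE rule chosen in item 1.

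Item 2 requires a relatedness assessment because a value that is no longer an AE would not otherwise receive one.

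The cost is a protocol amendment with IRB approval, one added sentence in the SAP and possibly an occasional extra SRC meeting. No visits or samples are added.
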